#### 6.1.9 **Duration of Therapy**

The duration of the active treatment portion of the study is 6 weeks, followed by an additional 3-week followup period. In order for participants to be included in the primary statistical analyses, they must complete the 6week treatment phase of the study (through to T8).

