## 5.7 Participant Withdrawal or Termination

#### 5.7.1 Reasons for Withdrawal or Termination

Participants are free to withdraw from participation in the study at any time upon request. An investigator may terminate participation in the study if:

• Any clinical adverse event (AE), laboratory abnormality, or other medical condition or situation occurs such that continued participation in the study would not be in the best interest of the participant

- The participant meets an exclusion criterion (either newly developed or not previously recognized) that precludes further study participation
- The participant fails to adhere to protocol requirements

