## 5.7.2 Handling of Participant Withdrawals or Termination

Every effort will be made to undertake the protocol-specified safety follow-up procedures to capture AEs, SAEs, and UPs. The investigator will attempt to obtain at a minimum safety/survival data on all participants lost to follow-up. If a participant is lost to follow-up, they study team will attempt to contact the participant up to 15 times by telephone, email, or text message. If the participant fails to respond, locators identified by the participant at screening will be contacted up to three times in the method specified by the participant. If participants withdraw, are terminated, or are lost to follow-up prior to the end of the 6-week treatment phase (prior to T8), they will not be replaced to maintain 48 randomized participants to complete the 6-week treatment phase (through T8) and their partial data will be handled according to the statistical analysis plan (SAP).

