## 15.4 Pregnancy Reporting

Pregnancy information on clinical study subjects is collected by the investigator. If a subject should become pregnant during the course of the study, the investigator or qualified designee will contact the IRB within 5 working days of the PI or qualified designee first becoming aware of the pregnancy.

Tilray Pregnancy Reporting Requirements: Every exposure during pregnancy (participant) should be reported on a Tilray SAE worksheet within 24 hours of the site becoming aware of the pregnancy as a case of special interest from the time of study enrollment to the end of study participation. If an SAE occurs in conjunction with the pregnancy, then the Tilray reporting timeframe for an SAE (24 hours) must be met. In the event of a pregnancy, administration of study medication will be discontinued, but all other follow-up data, including safety data, will be collected.

Pregnancies resulting in congenital abnormalities or birth defects in offspring meet the requirements for an SAE and will be collected, documented, and reported according to the procedures outlined above for SAEs.

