### 20.3 Description of Statistical Methods

### 20.3.1 General Approach

We recognize that the relatively small sample sizes proposed in the RCT are not likely to produce statistical significance, unless the effect sizes are remarkably high. We will carry out a full Mixed Model Repeated Measures (MMRM) statistical analysis in case CBD does perform so well. However, the main focus of the statistical analysis of the results of the trial will be to characterize the effect sizes and response rates across the various measurement domains and the profiles of individuals who are treatment successes. The intent to treat (ITT) population will contain all randomized patients who receive at least one dose of double-blind study medication and from whom at least one post-baseline (B1) efficacy measurement is obtained while on study medication. The efficacy analysis will be based on the ITT population. Two-sided hypothesis testing will be utilized. Tests with p-values less than or equal to 0.05 will be considered statistically significant, while those less than equal to 0.10 will be considered suggestive. Since this trial is the first use of this treatment for this diagnostic indication, no adjustments of p-values for multiple comparisons will be made. Thus, all control of type 1 error is contrast-wise. All confidence intervals will be two-sided with 95% confidence. Mean treatment effect, standard errors, and 95% confidence intervals will be derived from fully adjusted models on outcomes averaged across the treatment period. Cohen's d and p-values will be calculated from fully adjusted models with appropriately transformed outcome variables. For dichotomous drinking outcomes, prevalence rates will be calculated. Odds ratios (ORs) and p-values will be derived from logistic regression models including treatment group.

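### Section 6.1.9 restricts the primary analyses to participants who complete treatment through T8, contradicting the ITT efficacy population in 20.3.1 and the MMRM in 20.3.2

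*Combined protocol and SAP*

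**What the plan says.** Section 6.1.9 (Duration of Therapy) sets a condition for entering the main analyses: "In order for participants to be included in the primary statistical analyses, they must complete the 6week treatment phase of the study", with T8 as the end point of that phase. It does not separate one endpoint from another.

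Section 20.3.1 (General Approach) says "The efficacy analysis will be based on the ITT population". That population is everyone randomised who took at least one dose and "from whom at least one post-baseline (B1) efficacy measurement is obtained while on study medication". Section 20.3.2 then analyses drinks per day, and PCL-5 in the same way, with an MMRM on change from baseline. The primary contrast is at week 6 (T8), and contrasts are also taken at each earlier time point.

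Section 5.7.1 allows the investigator to end participation for an adverse event, a laboratory abnormality, a newly met exclusion criterion, or because "The participant fails to adhere to protocol requirements". Section 5.7.2 says of those who leave before T8 that "they will not be replaced to maintain 48 randomized participants to complete the 6-week treatment phase (through T8") and that "their partial data will be handled according to the statistical analysis plan (SAP"). Section 20.1 says a formal SAP is still to be written, before database lock and unblinding.

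On data after leaving, 5.7.2 says "Every effort will be made to undertake the protocol-specified safety follow-up procedures to capture AEs, SAEs, and UPs". Section 15.4 goes further for one case only, pregnancy: "administration of study medication will be discontinued, but all other follow-up data, including safety data, will be collected".

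**The concern.** The two rules define different primary efficacy sets. The set in 6.1.9 is chosen by what happens after randomisation, and several of the routes out of it (adverse events, laboratory abnormalities, failure to adhere) could be affected by CBD. A week-6 comparison of completers is therefore no longer a comparison of the groups as randomised. It also throws away week-2 and week-4 values from people who leave later, which the planned MMRM is able to use.

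This touches the trial's stated purpose. Section 20.3.1 says the main focus is to characterise effect sizes, and 20.4 says response will be characterised for planning confirmatory trials. A shifted effect size, or doubt about which population produced it, carries into that planning.

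**Working it through.** **Step 1. Put one participant through each rule.** Take someone randomised and dosed, with on-drug TLFB data and PCL-5 scores at weeks 2 and 4 (schedule in 7.1.7 and 7.3.3), who leaves in week 5.

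| Section | Result for this participant |
|---|---|
| 6.1.9 | Out of the primary analyses: T8 not completed |
| 20.3.1 | In the efficacy population: dosed, with a post-baseline value on drug |
| 20.3.2 | Week-2 and week-4 values can contribute to the MMRM |
| 5.7.2 | Not replaced; partial data left to the SAP |

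Both rules cannot define the same primary efficacy set. No text ranks them or labels either one a sensitivity analysis.

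**Step 2. How many participants might be involved.** The plan states no stopping rate, overall or by arm, so there is no plan figure to reproduce. The nearest guides are in 5.4: 85% follow-up at 6 months in a different population, and a 90% follow-up level at 10 weeks below which tracking is re-examined. These are follow-up rates, not treatment-completion rates. Used only as a guide:

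- 48 × 0.10 = 4.8
- 48 × 0.15 = 7.2

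**Step 3. Illustrate the shift.** Everything here except the arm sizes is assumed.

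- Arms: 30 CBD and 18 placebo (20.5.1).
- Stopping: 18% on CBD and 10% on placebo. 30 × 0.18 + 18 × 0.10 = 5.4 + 1.8 = 7.2 lost, the upper end of step 2.
- Stopping occurs after week 2 and depends on the standardised week-2 score Z (higher is worse): logit P(stop) = a + bZ, with b = 0.5 to 1.0 per SD and a set to give the stopping rate.
- Correlation r between week-2 and week-6 scores: 0.4 to 0.8. True treatment effect: zero.
- Completer-only shift = r × (E[Z | stays, CBD] − E[Z | stays, placebo]).

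| b | E[Z given stays], CBD 18% | E[Z given stays], placebo 10% | Difference | × r = 0.4 | × r = 0.8 |
|---|---|---|---|---|---|
| 0.5 | −0.087 | −0.049 | −0.038 | −0.015 | −0.030 |
| 1.0 | −0.157 | −0.091 | −0.066 | −0.027 | −0.053 |

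The range is 0.015 to 0.053 SD, in favour of the arm with more stopping. The standard error of a simple two-group contrast is √(1/30 + 1/18) = 0.298 SD, so the shift is 0.015/0.298 = 5% to 0.053/0.298 = 18% of it. With equal stopping rates and the same b in both arms the two expectations are equal and the shift is 0. With b = 0 it is also 0.

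**Step 4. What keeping partial data achieves.** In step 3 stopping depends only on an observed value, and a likelihood model that includes everyone's observed data then removes the bias. That is a property of the assumption, so the other case was checked too. The rates, b and r were kept, but stopping was made to depend on the unobserved week-6 score (large simulation; missing week-6 mean estimated from the week-2 regression among those who stay). The completer-only shift was 0.038 to 0.067 SD and the all-data shift 0.014 to 0.056 SD. Partial data reduce the bias in that case but do not remove it.

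**The case against.** The best reply is that 20.3.1 and 20.3.2 are the statistical section and already specify ITT with MMRM, while 6.1.9 is one sentence under a treatment-duration heading. On this view the SAP, due before unblinding, will settle the matter blind. Part of this stands. A reader might infer that the sponsor is free to pick the better of two results after seeing them, and the documents do not support that if 20.1 is followed. But 6.1.9 is current text, nothing says 20.3.1 overrides it, and deferring partial data to a future SAP does not cancel a rule that excludes those participants.

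Other stronger readings are tempting and go too far:

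- *Intolerance means exclusion.* Section 6.1.8 provides for dose reduction and for staying on the highest tolerable dose to the end of the study. Poor tolerability need not lead to non-completion.
- *Safety is analysed in completers only.* The wording of 6.1.9 is loose enough to suggest it, but 20.3.2 and 20.3.4 analyse adverse events in the entire sample.
- *The on-drug condition in 20.3.1 is an equally serious filter.* It asks for one value and does not discard later off-drug data. The first dose is taken on site (6.3.1) and drinking is recorded from T2, so few would be lost. It matters mainly for PCL-5, first measured after baseline at week 2.
- *Only safety data are ever collected after leaving.* For those lost to follow-up, 5.7.2 sets safety and survival data as a minimum, not a ceiling, and 20.3.5 counts stopping the intervention separately from stopping follow-up. What is missing is a general instruction to continue efficacy assessments off drug.

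Section 6.1.9 also leaves open whether someone who stops drug but attends T8 counts as a completer, so the number excluded is uncertain even under its own rule.

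**Conclusion.** The contradiction between 6.1.9 and 20.3.1/20.3.2 is clear on the text, and as written 6.1.9 should not stand. It would exclude randomised participants on post-randomisation events and waste data that the chosen model can use.

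The size of the resulting bias cannot be derived from the documents and is probably small. The 0.015 to 0.053 SD range rests wholly on the assumed stopping rates, stopping mechanism and correlation, and on a true effect of zero. A reader might infer that a completer analysis is certain to flatter CBD. The documents give no arm-specific stopping rates, so neither the existence nor the direction of a shift is established. Nor should the ITT analysis be described as free of bias: that holds if stopping depends on observed values, and otherwise the bias may only be reduced. Confidence is high in the textual conflict and low in any particular figure.

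**What to change.** 1. **Section 6.1.9 (main change).** Delete the requirement to complete through T8. Replace it with: *Efficacy analyses use the ITT population in 20.3.1; safety analyses use the entire sample as in 20.3.2.* A completer analysis may remain if labelled as a sensitivity analysis.
2. **Section 20.3.1 (secondary).** Remove the on-drug condition from the clause on post-baseline measurement, so that any dosed participant with a post-baseline value enters the MMRM. This probably affects few people, mainly for PCL-5. The dose and one-value conditions remain, so it narrows the post-randomisation filter and does not abolish it.
3. **Section 5.7.2 (secondary).** State that participants who stop study drug without withdrawing consent continue the scheduled TLFB and PCL-5 through T8, as 15.4 already provides after pregnancy.

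The cost is about one sentence in each section, plus self-report assessments already on the schedule for those who stop early (roughly 5 to 7 people if the 5.4 follow-up figures are a fair guide). Sample size and visits do not change. The downside is that some off-drug data enter the estimate, which may then understate the effect of CBD while it is being taken.

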Participants in [name] clinical trial "Leveraging Biomarkers for Personalized Treatment of AUD Comorbid with PTSD" (IRB # s18-01405) who are determined to be ineligible will be evaluated for eligibility in this trial. Consenting participants' data will be linked to this study and procedures completed under the Biomarkers trial will not be duplicated for this trial except at PI or co-Investigator discretion.

Based on successful recruitment in current and past AUD and PTSD trials at NYULMC, we do not expect any significant barriers to recruitment. If recruitment lags, strategies would include altering staffing patterns and increasing advertisement and outreach to clinical programs. To maximize rates of completion of the follow-up visit, we will follow procedures that have been successful in retaining patients with similar demographics, e.g. drug using emergency department patients, for whom we have achieved follow-up rates of 85% at 6 months. If follow-up rates at 10 weeks are below 90%, we will reexamine our tracking procedures, and consider altering the reimbursement and/or completing community-based follow-ups.

We expect the population to be approximately 50% male, 50% female; 7% Hispanic, 60% Non-Hispanic Caucasian, 30% Non-Hispanic African American, and 3% other.

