# 20 Statistical Considerations

## 20.1 Statistical and Analytical Plans (SAP)

A formal SAP will be developed prior to database lock and unblinding.

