### 20.3.2 Analysis of the Primary Endpoint(s)

For Hypothesis 1a, Safety and tolerability, the frequency of adverse events will be analyzed for the entire sample at all time points, tabulated for each treatment group, and compared using chi-squared tests. The safety analysis will be largely descriptive of outcomes for the entire study population. The incidence of AEs will be summarized by system organ class, preferred term, the likelihood of its relationship to the treatment, and severity for each treatment group. Clinical laboratory data will be summarized by type of test. Frequency and percentage of patients whose values fall outside of reference ranges will be presented for each measurement.

For Hypothesis 1b, Alcohol Use. The Primary outcome measure, number of drinks per day, will be analyzed with an MMRM to assess differences in change from baseline. The primary contrast is change from baseline (B1) at week 6 (T8). The model at each time point will include terms for treatment, time and treatment by time interaction as factors and the baseline value for each score as a covariate. Parameter estimation will be based on REML and to begin an unstructured covariate matrix will be used. If the model fails to converge, the form of the covariance matrix will be chosen based on Akaike's Information Criteria, and Schwarz' Bayesian Criterion. Model-based LS means will be obtained for change from baseline to each time point for each treatment group. At each time point, contrasts between CBD and placebo will be obtained. Secondary alcohol use measures will be tested with MMRM sequentially in a closed testing union intersection paradigm in the order listed in section C.8.3. Validity of the p-value will extend until the first test fails to have a p-value smaller than a two-sided alpha of 0.05. The analyses will continue for all measures but the resulting p-value will be nominal.

For Hypothesis 2, PTSD symptoms, the primary outcome measure, total score of the PCL-5, will be analyzed in the same way as the primary outcome for alcohol use. The primary contrast is change from baseline (B1) at week 6 (T8).

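### Section 6.1.9 limits the primary analyses to six-week completers, section 20.3.1 bases efficacy on a modified ITT set, and nothing in the plan says which governs.

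*Combined protocol and SAP*

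**What the plan says.** Section 6.1.9 (Duration of Therapy) sets a condition: for "participants to be included in the primary statistical analyses, they must complete the 6week treatment phase of the study", that is, through T8. The sentence is not labelled as a completers, per-protocol or sensitivity analysis.

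Section 20.3.1 (General Approach) defines a different set: "all randomized patients who receive at least one dose of double-blind study medication and from whom at least one post-baseline (B1) efficacy measurement is obtained", with that measurement taken on study medication. It then states: "The efficacy analysis will be based on the ITT population".

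Section 20.3.2 names drinks per day and the PCL-5 total score as primary outcomes. Each is analysed by MMRM, with change from baseline at week 6 (T8) as the primary contrast. It adds: "Model-based LS means will be obtained for change from baseline to each time point for each treatment group".

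Section 5.7.2 says that participants who leave before T8 are not replaced and that the SAP will cover their partial data. Section 20.1 says of that document: "A formal SAP will be developed prior to database lock and unblinding".

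**The concern.** Both rules claim the same two analyses. Someone who gives drinking and PCL-5 data at week 2 and then leaves is in the primary set under 20.3.1 and out of it under 6.1.9. The primary analysis set is therefore not defined, and whoever writes the SAP could cite either section.

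The choice matters because completing treatment happens after randomisation. If people leave CBD for different reasons than they leave placebo, the completers in the two arms are no longer comparable, and the estimated difference can be biased in either direction. Section 20.3.1 makes estimating effect sizes the main purpose of the analysis, and section 20.4 ties the design to planning confirmatory trials. Bias in the estimate therefore matters even if significance is unlikely. The completers rule would also discard the early visits of those who leave, which the MMRM could use.

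The rule concerns those who leave before T8. Section 6.1.8 keeps participants on a reduced dose in treatment, so dose reduction alone does not exclude anyone.

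**Working it through.** **1. The conflict in the text.** No arithmetic is needed.

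| | Section 6.1.9 | Section 20.3.1 |
|---|---|---|
| Applies to | Primary statistical analyses | Efficacy analysis |
| Entry rule | Complete treatment through T8 | One dose and one post-baseline efficacy value on study medication |
| Drinks per day, PCL-5 (primary and efficacy) | Covered | Covered |
| Leaves after week-2 assessments | Out | In |

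Sections 5.7.2 and 20.1 do not settle it, because the first defers to an SAP that the second says is still to come.

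**2. How many participants.** The plan gives no dropout rate by arm and no figure of its own to reproduce. Its only retention figures are in section 5.4. One is a trigger: "If follow-up rates at 10 weeks are below 90%, we will reexamine our tracking procedures". The other is a past 85% follow-up rate at 6 months in a different setting. I assumed dropout of 10%, 15% and 20%:

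- 10%: 0.10 × 48 = 4.8, about 5
- 15%: 0.15 × 48 = 7.2, about 7
- 20%: 0.20 × 48 = 9.6, about 10

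These are upper bounds for PCL-5. Its first post-baseline assessment is at week 2, so anyone who leaves earlier is out of that analysis under both rules.

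**3. Size of the bias (simulation).** From the plan: 30 CBD and 18 placebo. My assumptions: no true effect; baseline, week-2 and week-6 values with unit SD and correlation 0.6; dropout after week 2; 20,000 replicates per scenario. Higher scores are worse, so a negative bias favours CBD. Two estimates of the week-6 difference were compared:

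- Completers: week 6 regressed on arm and baseline, in completers only.
- All data, missing at random: week 2 regressed on arm and baseline in everyone; week 6 regressed on arm, baseline and week 2 in completers; the arm effect is the direct coefficient plus the week-2 slope times the week-2 arm effect.

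In the table, the worst means those with the highest week-2 values.

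| Who leaves | Dropout CBD / placebo | Completers bias (SD units) |
|---|---|---|
| Worst from CBD, random from placebo | 10% / 10% | -0.051 |
| | 15% / 15% | -0.068 |
| | 20% / 20% | -0.090 |
| Random from CBD, worst from placebo | 10% / 10% | +0.050 |
| | 15% / 15% | +0.067 |
| | 20% / 20% | +0.086 |
| Worst from both arms | 20% / 20% | 0.000 |
| | 20% / 10% | -0.042 |
| | 10% / 20% | +0.041 |

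The all-data estimate stayed between -0.002 and +0.003 throughout. At 20% in the first scenario, correlations of 0.4, 0.6 and 0.8 gave completers bias of -0.089, -0.090 and -0.064. A separate re-run with 8,000 replicates agreed within simulation error.

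**4. Bias against precision.** At 20% dropout the SD of the estimate is 0.274 (completers) and 0.276 (all data), against 0.242 with no dropout. The two rules lose almost the same precision, so the difference between them is bias. The largest bias is 0.090 / 0.274 = 0.33 of the SD. By normal approximation, a shift of 0.33 moves the two-sided 5% error to Φ(-1.96 + 0.33) + Φ(-1.96 - 0.33), or about 6.2%.

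**The case against.** **Section 20 should prevail.** It is the statistical section and is explicit about efficacy. Section 5.7.2 expects partial data to be handled, and the MMRM is designed to use them. On this view 6.1.9 is a stray sentence in a dosing subsection, and the promised SAP would settle it. This is the likelier intention, but no text says so, and 6.1.9 uses mandatory wording about the primary analyses. It is a reason to remove the sentence.

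**The simulation is built to show bias.** Several points here stand.

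- Having exactly the worst 20% leave CBD is an extreme. With a graded dependence on the week-2 value (log-odds slope of 1 per SD), the bias is -0.052 at 20% and -0.025 at 10%.
- The all-data estimate is nearly unbiased because dropout was made to depend only on observed values. If it depends on the unseen week-6 value, both estimates are biased at 20%: -0.234 for completers and -0.207 for all data.
- Even the largest missing-at-random figure, 0.09 SD, is about one tenth of the 0.939 detectable effect in section 20.4 (0.090 / 0.939 = 0.096). That 0.939 is itself a separate problem: 30:18 gives 0.853 by t test. It fits 25:15, but the documents never state 40 participants, so it supports neither rule.

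**The 20.3.1 set is not pure ITT either.** It also requires a post-randomisation event, an on-treatment efficacy value. That is true, but the condition is much weaker than six-week completion.

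A completers-only MMRM would still run, and would still use completers who missed an intermediate visit. What it loses is the data of those who leave.

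**Conclusion.** The concern holds. The plan gives two incompatible entry rules for the same two primary efficacy analyses and does not say which applies. This rests on the text alone.

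Read literally, 6.1.9 also clashes with the safety analysis. The Protocol Summary lists adverse events as a primary endpoint, and section 20.3.2 analyses them in the entire sample. A completion rule would remove those who stopped because of an adverse event.

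The bias figures are an illustration under assumed dropout that is missing at random: zero when the worst leave both arms at the same rate, and up to about 0.09 SD in either direction when the arms differ. Graded dropout brings the larger figures down to roughly half. Using all available data removes this bias only if dropout depends on observed values; otherwise both approaches are biased, completers slightly more.

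It should be corrected before unblinding, because an open choice of analysis set is a choice that could be made after results are seen.

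**What to change.** - Delete the completion requirement in section 6.1.9, or relabel it as a supportive completers analysis.
- State in section 20 and in the SAP, before unblinding, that both primary efficacy analyses use the section 20.3.1 population in assigned arms, with all available post-baseline values through T8 in the MMRM.

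Removing the rule from the primary analyses also clears the clash with the entire-sample adverse event analysis in section 20.3.2.

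The cost is one sentence deleted or relabelled and one added. The values come from visits already planned, and no dose or clinical rule changes.
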